7.5.1 Informed Consent

Please refer to section 6.3 for detailed information on Informed Consent.

7.5.2 Medical History

General Medical Systems History

A pre-existing health history including current medications will be collected at the first visit to ascertain a baseline prior to vaccination. The health history and medications/exposures will be updated at each subsequent visit. The baseline health assessment will be sufficiently detailed to confirm eligibility to participate and to identify a baseline for appropriate management of any SAEs that are reported.

Focused Medical History:

HIV diagnosis date & mode of acquisition if known; current HIV treatment, abnormal Pap tests, colposcopies, and treatments; history of genital warts and treatments; STIs; reproductive history will be ascertained at the Month 0 visit and updated at subsequent visits.

Please ensure at the comprehensive medical history is taken and documented prior to vaccination.

7.5.3 Brief Physical Assessment

The brief physical assessment will include: height (month 0 only), weight (month 0 and month 12 only), and temperature. Temperature should be assessed prior to each vaccination.

7.5.4 Clinical Laboratory Investigations

Clinical blood samples will be collected, handled, processed, and analyzed at site local laboratories as per local practices. Current HIV and general health status will be determined by abstraction of clinical chart data and routine clinical laboratory tests (CBC, liver enzymes, renal function, CD4 T cell subsets, and HIV RNA quantitative PCR [viral load]).

7.5.5 Study Blood Work

Ensure all blood tubes are clearly labeled with the 5-digit PID#, collection date, and visit number. Study blood work must be collected within 24 hours of the study self-collected HPV DNA sample. For complete serology sample protocol, see Laboratory Protocol.

7.5.5.1 Serum Antibody Testing

Whole blood by venous route is to be collected observing aseptic conditions into one 10mL red top Serum Vacutainer (non-heparinized, non-EDTA, non-serum separator) tube. Specimens should be placed upright and allowed to clot for 30 to 60 minutes. After the sample has clotted it should then be

refrigerated at 2-8 degrees Celsius until centrifuged. Samples are to be centrifuged within 24 hours of collection and according to manufactures specification to allow for complete separation of serum. Serum is to be aliquoted using a plastic pipette into 2 cryovials, each containing a minimum of 2.0 mL and then frozen between -60 and -80 degrees Celsius at the investigative site until recalled by the Study Coordinating Centre. One aliquot will go to the BC Women's Research Lab (Women's Health Research Institute) for storage, and the other will be transferred to the Merck Laboratory for in-house serotesting. There, serum anti-HPV6, 11, 16, 18, 31, 33, 45, 52, and 58 immunoglobulin levels will be measured using competitive Luminex immunoassay (cLIA).

7.5.5.2 Immune Response Sub-Analysis

Peripheral blood mononuclear cells (PBMCs) will be collected at month 0 and month 7 from a subset of 60 participants in each arm of the trial (120 participants total) for future exploration of the nature of the immune response in women with and without HIV viral load suppression (funding for sample analysis to be applied for in future). 30mls of whole blood by venous route is to be collected observing aseptic conditions into three 10mL heparin tubes.

7.5.6 β HCG Pregnancy Test

All participants are to provide a fresh urine sample for a dipstick pregnancy test at the first visit and before (same day) the administration of each of the 3 doses of the HPV vaccine. Results of the urine dipstick test must be available and negative prior to proceeding with the vaccination. Alternatively, a negative serum pregnancy test result done the day of the vaccination is acceptable.

Participants will be provided with counseling regarding avoidance of pregnancy. Effective birth control measures for this study are to include: birth control pill, IUD, Depo Provera, hormonal implants, male or female condom with or without spermicide, diaphragm or sponge with or without spermicide, or abstinence.

7.5.7 HPV Self-Sampling Questionnaires

Questionnaires elucidating attitudes towards HPV self-sampling will be administered at the Month 0 visit and at study end to explore attitudes towards HPV self-sampling before and after using this testing methodology within the study. The survey will assess attitudes regarding acceptability, comfort, and willingness to use this sampling methodology in future.

7.5.8 Self-Collected Vaginal Swab Samples

Samples will be clearly labeled with the 5-digit PID#, collection date, and visit month. Ideally, HPV DNA samples should be collected within 24 hours of the study blood work sample. Samples should be stored at room temperature until received by the site laboratory.

Participants will be provided one dry swab and instructed how to self-collect a vaginal specimen using a standard script and diagram. Sample collection will occur in a private space within the clinic where the study visit is occurring and will be returned to study staff immediately. Participants will collect one sample for testing. An extra swab will be provided in case the original swab is dropped or damaged. The sample will be aliquoted into two vials (1 analysis sample, one retention sample). For full sample processing procedures, see Laboratory Protocol.

If the participant is menstruating at the time of their study visit, the swab collection will be re-scheduled for a later date or the participant will be invited to take the sample collection kit home to collect when not menstruating. Participants will be given instructions and postage paid mailing materials to return the swabs to the study centre. Participants will be given the option to have a physician or nurse practitioner collect the swabs for them if they do not wish to self-swab.

7.5.9 Post-Vaccine Diaries

Following their first, second, and third HPV vaccine doses, participants will be asked to complete a 14-day Post-Vaccine Symptom Diary. They will be instructed to fill out the diary with details regarding any symptoms that they experience following their vaccination. The diary may be offered in two formats: paper or a REDCap survey. If the diary is in paper format, participants will be provided with a stamped envelope to return it to the study site or they may bring it with them to their next study visit.

7.5.10 Concomitant Medications and Exposures

Concomitant medications for the purpose of this study, to be documented, are to include: antiretroviral therapy, other vaccines, prescriptions, over the counter medications, hormonal, herbal, vitamin, alternative and complementary therapy; exposures will include: use of drugs of addiction, tobacco, and alcohol.

At each visit, participants will be asked about their medication usage/exposures. All concomitant medications and exposures taken at any time during the period starting with the first visit will be collected. Information to be collected should include: name of medication (generic name or trade name for combination medications), medical indication, total daily dose, and route, start and stop dates. PRN medications may be listed as PRN for total daily dose.

If a participant is on and off a treatment throughout the study, please ensure that the start and stop date indicate the time the participant was on and off treatment. Additionally, if the dosages change a stop date should be entered for the previous dosage and a new entry made for the start of the new dosage.

For exposure to drugs of addiction, tobacco, and alcohol use, the most basic description, for example, THC, heroin, cocaine, tobacco, ETOH. For frequency, have the participant estimate usage per day, week, or month.

Participants' antiretroviral therapy use over the course of the study will also be captured.

7.5.11 BC Cancer Registry Linkage

For participants who provide specific consent, a linkage the BC Cancer Registry will be performed to determine pre-cancer or cancer diagnoses. First name, last name, full date of birth and PHN will be used for this linkage. This linkage may be done a number of years after the study is finished.

For sites that do not have a Provincial cancer registry, cancer outcomes may be obtained by clinical chart review.

The BCCDC Data Linkage and Destruction Plan, is as follows:

1. BCCDC Data Guardian creates a folder in \\Phsabc\root\BCCDC\Groups\public\DROPBOX
2. NOVA Team prepares the data set to be linked, encrypts dataset and shares to BCCDC via the above network folder
3. NOVA Team shares encryption password with designated BCCDC Data Guardian
4. Data Guardian adds the NOVA dataset to designated folder in the BCCDC Central Data Repository
5. Data Guardian unencrypts the NOVA dataset
6. Data Guardian links the NOVA dataset and BCCDC dataset using personal identifiers (PHN, DOB, name) to create Combined Dataset
7. Data Guardian replaces PHN with Study ID, removes DOB and name
8. Data Guardian encrypts de-identified Combined Dataset and shares with designated NOVA Researcher via the folder above
9. NOVA Researcher adds file to access limited dataset on the PHSA Network
10. NOVA Researcher confirms Combined Dataset is ok, notifies Data Guardian
11. Data Guardian destroys BCCDC and NOVA datasets

NOVA Researchers will retain de-identified combined dataset for 15 years post publication of data (in keeping with section 8.6.A of the application)

At or before 15 years after the end of the study, NOVA Researchers will destroy the dataset and notifies BCCDC and NOVA Teams of its destruction.

8.0 HPV VACCINE ADMINISTRATION

1. Characteristics

The vaccine to be used in this trial is GARDASIL®9. GARDASIL®9 (Nonavalent Human Papillomavirus [Types 6, 11, 16, 18, 31, 33, 45, 52, 58] Recombinant Vaccine) is a recombinant nonavalent vaccine that protects against HPV.

2. Vaccine Acquisition

Merck will provide commercially available lots of GARDASIL®9 to investigative sites following cold chain procedures. Where available, sites will use free, publicly-available GARDASIL®9 vaccines prior to the Merck lots.

3. **Vaccine Storage**

Vaccine will be stored at 2-8 degrees Celsius, do not freeze, and protect from light. The vaccine is to be stored in the local hospital pharmacy, or secure continuously monitored refrigerator accessible to study clinical staff. Demonstration of stable refrigeration temperatures for 1 week prior to vaccine storage in the designated study refrigerator is required. Ongoing documentation of adequate cold chain must be kept by each site.

4. **Allocation**

Supplied vaccine is open label.

5. **Accountability**

Vaccine accountability must be maintained throughout the clinical trial. All vaccines arriving at the site will be entered onto a vaccine accountability log provided by the Study Coordinating Centre. All vaccines used, wasted, replaced, expired, or destroyed is to be tracked on the accountability log.

6. **Dosage and Administration**

Doses are given at 0, 2 and 6 months (in the routine group), and 0, 6, and 12 months (in the extended group). Doses are to be given intramuscularly in the deltoid region of the upper arm or in the higher anterolateral area of the thigh. Injection should occur using a 22 or 23-gauge needle, one inch in length. The full recommended dose of 0.5ml must be used.

The vaccine made available for this study will be in single use vials. A separate sterile syringe and needle must be used for each individual. The vaccine should be used as supplied with no dilution or reconstitution necessary.

Prior to injection, the vaccine (vial/syringe) is to be thoroughly agitated immediately prior to administration to ensure suspension of the vaccine. The fluid should be white and cloudy after agitation. Inspect the fluid for particulate matter and discoloration prior to administration. Discard the vaccine if particulates are present or if it appears discolored and document on the vaccine accountability log.

Withdraw the 0.5-mL dose of vaccine from the single-dose vial using a sterile 22 or 23-gauge needle and syringe free of preservatives, antiseptics, and detergents. Once the single-dose vial has been penetrated, the withdrawn vaccine should be used promptly, and the vial must be discarded. Replace the needle for administration.

7. **Documentation**

Clinical staff will document the date, time, and location of vaccine administration in the Participant's clinical chart or electronic medical record. Clinical staff will also indicate whether the study vaccine or publicly available vaccine was given. Research staff will

transcribe this information into the study case report form. Ensure that the vaccine usage has been documented on the vaccine accountability log. Ensure clinical staff are aware that a participant has received a dose of vaccine for documentation in clinical records.

8. Replacement

Replacement of vaccine, if necessary, will be from open label stock. Documentation of wasted and replaced vaccine is necessary on the vaccine accountability log.

9.0 ADVERSE EVENTS AND SERIOUS ADVERSE EVENTS

Please ensure that a comprehensive medical history is taken and documented prior to vaccination to ensure that only new adverse events are captured as AEs.

1. Adverse Events

All adverse events will be collected during the vaccination phase of the study for up to 14 days following a vaccine. Documentation should include, diagnosis (or symptom if not diagnosed), start and stop dates, intensity (using the DAIDS AE grading table), and treatments. Narrative notes should detail the event and possible contributing factors. All AEs collected in the vaccination phase of the study (up to 14 days following a vaccine) must be assessed as to their relationship to the vaccine and signed off by a site investigator.

All newly diagnosed chronic illnesses; worsening, increase in severity, or frequency of pre-existing conditions; or medically significant illnesses occurring more than 14 days after the administration of the vaccine will be collected throughout the entire study as updates to the general medical history.

2. Serious Adverse Events

Serious adverse events (AEs), medically attended AEs, and provincially reportable AEs following immunization will be collected. Serious AEs will be defined per GCP-ICH guidance and all will be collected regardless of presumed relatedness and/or expectedness. AEs will be reviewed at each study visit, and participants will have emergency contact details for the local research team to report events between visits.

9.2.1 Definitions

A SAE is any untoward medical occurrence that:

- Results in death
- Is immediately life-threatening
- Requires inpatient or prolongation of existing hospitalization
- Results in persistent or significant disability or incapacity
- Is a congenital anomaly or birth defect in the offspring of a study participant
- Other medical events that may not be immediately life-threatening, result in death or hospitalization but may be significant or jeopardize the participant or require medical or surgical intervention to prevent one of the defined

SAEs as an outcome

All SAEs will be recorded, regardless of time since vaccination.

9.2.2 Reporting Time Period

All SAEs occurring during the study must be recorded and reported to the Study Coordinating Centre whether or not they are considered vaccine-related. All SAEs are considered severe. The investigator must make a determination of causality using clinical judgment and after considering and investigating alternative causes such as underlying conditions, concomitant therapies, other risk factors and the temporal relationship.

SAE reports will be faxed to [name] at the Study Coordinating Centre and the Canadian HIV Trials Network (CTN) within 24 hours of discovery or notification to the study centre of an SAE. Site investigators are obligated to notify their REB as per local reporting requirements.

SAE Notification:
[name] (fax#) [contact] (24 hours)
AND CTN (fax#) [contact] (48 hours)

The Study Coordinating Centre will acknowledge receipt of the faxed SAE form. Site Investigators should also report SAEs to their provincial adverse event reporting centre as would occur when administering any routine licensed vaccine.

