1. To determine if 2 doses of 9vHPV vaccine are non-inferior to 3 doses in WLWH for the additional 9vHPV types not in the primary outcome, we will evaluate serologic response by comparing peak anti- HPV6/11/31/33/45/52/58 GMTs individually and seroconversion rates with 95% CI at 7 months in both groups using linear and logistic regression, respectively, adjusted for HIV viral load, CD4+ T cell count, and age.
2. As the world is moving towards one-dose HPV vaccine schedules, we will take the opportunity to collect preliminary data on the peak one-dose antibody response at month 1. These data will inform the sample size calculation for a future one-dose trial, as appropriate, and will be reported as anti-HPV16/18 GMTs with 95% CI.
3. To evaluate significant adverse events, the proportion (and 95%CI) of participants who experience significant adverse events will be calculated for the entire study population, and also by group. The types and severities of adverse events will be described.
4. To address vaccine efficacy, we will calculate incidence rates of abnormal cervical cytology and histology (HSIL), and breakthrough persistent HPV infection. HSIL will be described with Kaplan-Meier curves. If sufficient numbers of each are observed, Kaplan-Meier curves will be calculated by age range (21-30, 31-39, 40-55, >55), CD4 count (<200, 200-500, >500), HIV viral load (detectable vs. undetectable), and prior HPV status. Persistent HPV will be described by type of HPV, high vs. low-risk, and vaccine type or not, using Kaplan-Meier curves for HPV acquisition and frequencies and percentage for persistent infections. Given the capability to intervene with early pre-cancerous changes in the cervix, we cannot ethically use cervical cancer as an end point but other efficacy endpoints are critical for an HPV vaccine study as an immune correlate of protection is unknown.
5. To assess the uptake of HPV vaccination of WLWH, a screening log will be kept by each study site to track how many WLWH aged 18-45 were not eligible to participate in the study due to having already received an HPV vaccine. The proportion of women who were previously vaccinated will be calculated for the population of women aged 18-45 at each site and across the country.

6. **Planned Subgroup Analyses**

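### Section 9.2.2 labels every SAE severe, which conflates seriousness with intensity and is not reconciled with the DAIDS grading in Section 9.1

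*Protocol*

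**What the plan says.** Four parts of the protocol bear on this.

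- **Section 9.1 (Adverse Events).** For adverse events up to 14 days after a vaccine, sites document "intensity (using the DAIDS AE grading table", along with diagnosis, dates and treatments. Medically significant illnesses after day 14 are recorded as updates to the medical history, and no grading is specified for them.
- **Section 9.2.1 (Definitions).** An SAE is defined by consequence. The criteria include "Results in death", "Is immediately life-threatening" and "Requires inpatient or prolongation of existing hospitalization", and also "Other medical events that may not be immediately life-threatening, result in death or hospitalization but may be significant". None sets a minimum intensity. Collection is not tied to the 14-day period: "All SAEs will be recorded, regardless of time since vaccination".
- **Section 9.2.2 (Reporting Time Period).** Without qualification: "All SAEs are considered severe".
- **Sections 3.0 and 13.5.** Severity of adverse events is part of exploratory objective 6, and the planned analysis says "The types and severities of adverse events will be described".

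**The concern.** Seriousness and severity are different attributes. Seriousness records what an event led to, such as death, admission or disability. Severity records how intense the event was. An event of moderate intensity can be serious because it led to a hospital stay, and an intense event need not be serious. Section 9.2.2 derives the second attribute from the first.

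This is a recording instruction to sites, so it matters before any analysis plan comes into play. If sites follow it literally and do not grade SAEs, there is no intensity value to tabulate later. What is at stake is the usefulness of the severity description for the most important safety events, in a population for which the protocol itself says data on this vaccine are limited.

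**Working it through.** The protocol states no SAE rate and no severity distribution, so there is no figure to reproduce. The check is mainly a comparison of the sections.

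**1. Does the SAE definition imply severe intensity?** No. The criteria in Section 9.2.1 run from death, through admission to hospital, to significant events that are neither fatal, nor life-threatening, nor hospitalised. One criterion is a birth defect in a participant's offspring, for which a severity label does not describe an intensity in the participant at all. Nothing in the definition ensures that each SAE would be graded severe, no lower and no higher.

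**2. Where do the two instructions meet?**

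| Timing of SAE | Section 9.1 | Section 9.2.2 | Result |
|---|---|---|---|
| Up to 14 days after a dose | DAIDS intensity grade | Severe | Two instructions, no stated precedence |
| After day 14 | No grading specified | Severe | Blanket label is the only severity instruction |

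Each participant is scheduled for three doses, so the period of direct conflict is at most 3 × 14 = 42 days. Over 24 months, about 730 days, that is 42 / 730 = 5.8% of follow-up. The direct contradiction is therefore narrow. For the rest of follow-up the fault is different: a constant label stands where a grade would be needed.

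**3. What does the label do to the severity summary?** Followed as written, 100% of SAEs are severe by construction, so severity among SAEs says nothing beyond the SAE count.

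For the table of all adverse events, let *s* be the share of adverse events that are SAEs and *m* the share of SAEs whose graded intensity would not be severe. The share of adverse events carrying a label that differs from their grade is *s* × *m*. Neither quantity is in the protocol. With assumed values, in percentage points:

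| *s* | *m* = 10% | *m* = 30% | *m* = 50% | *m* = 80% |
|---|---|---|---|---|
| 1% | 0.1 | 0.3 | 0.5 | 0.8 |
| 2% | 0.2 | 0.6 | 1.0 | 1.6 |
| 5% | 0.5 | 1.5 | 2.5 | 4.0 |
| 10% | 1.0 | 3.0 | 5.0 | 8.0 |

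The range, 0.1 to 8.0 points, shows scale only. It counts mislabelling in both directions, so the net change in the share called severe could be smaller.

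**4. What is not touched?** The label does not decide whether an event counts as an SAE or whether it is reported, since all SAEs are reported whatever their relation to the vaccine. The month 7 antibody comparison does not use it.

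**The case against.** The best defence is that the sentence sits among reporting instructions and may be only a cautious convention for handling SAE reports. It does not say that the DAIDS grade is replaced, that severe is entered in the intensity field, or that the label feeds the severity summary. An SAE within 14 days of a dose is still an adverse event under Section 9.1 and should still be graded. That is fair as far as it goes. But the text nowhere limits the label to reporting or says that SAEs keep their grade. Because all SAEs are reported anyway, the sentence adds no protection. For SAEs after day 14, Section 9.1 requires no grade to fall back on.

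Three stronger readings are tempting, and the documents do not support them.

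- *That Section 9.2.2 overrides the DAIDS grading and falsifies the severity distribution.* The protocol does not say which instruction prevails. It shows only that the two are unreconciled.
- *That the most extreme events are hidden.* Death and immediate threat to life are separate SAE criteria, so these events remain identifiable whatever their severity label. The protocol does not tie severe to a particular DAIDS grade, and the sentence could even be read as a minimum.
- *That a definite number of women would be misclassified.* Suppose 2% to 8% of 450 women had an SAE (9 to 36 women) and one third were not severe: that gives 3 to 12. If the one third is instead varied from 10% to 80%, the range becomes 9 × 0.10 = 0.9 to 36 × 0.80 = 28.8. All these rates are assumptions, so the count is not a finding.

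It is also fair to say that the layout of safety tables belongs in an analysis plan, which is not shown. That answers any complaint about tabulation, but not one about what sites are told to record.

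**Conclusion.** The point holds as a minor one. The sentence in Section 9.2.2 confuses seriousness with severity, conflicts with Section 9.1 in the 14 days after each dose, and is the only severity instruction for SAEs after that. Because SAEs are defined by outcome alone, the label misstates the intensity of any SAE that would be graded otherwise, and it leaves severity among SAEs without information.

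The damage is limited to the severity part of one exploratory, descriptive analysis. Within SAEs the loss is complete if the sentence is followed literally. In the table of all adverse events it is probably small, though its size depends on an SAE rate and an intensity mix that the protocol does not give. The conclusion itself rests on the wording of the sections and needs neither of those assumptions.

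**What to change.** Delete the sentence in Section 9.2.2. State in its place that every SAE, whenever it occurs, has its intensity graded on the DAIDS table already named in Section 9.1, and that seriousness is recorded as a separate field.

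The cost is one sentence in the protocol and a check that the case report form and SAE form hold both fields. SAEs already recorded under the blanket label would need an intensity grade added from their source documents. Nothing changes for participants, for the reporting of SAEs or for the sample size.
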